### 11.5 Safety monitoring and determination of excess toxicity

To minimize risk to patients on study, we will perform interval analyses to determine if excess treatment-associated toxicity is observed during the trial. Toxicity may occur due to treatment with flotetuzumab, DLI administration, or unknown factors. Since GVHD may be an expected result of DLI, there will be separate stopping rules for excess non-GVHD toxicity and for GVHD toxicity.

#### 11.5.1 Excess non-GVHD toxicity

Excess non-GVHD toxicity will be defined as a combined incidence of > 20% of any of the following:

- $\geq$  Grade 3 non-hematologic AE at least possibly attributable to protocol treatment, with the following exceptions:
  - Grade 3 fatigue, asthenia, fever, constipation or anorexia (if anorexia does not result in hospitalization, tube-feeding or use of total parenteral nutrition [TPN])
  - Grade 3 nausea, vomiting or diarrhea not requiring tube feeding, TPN, or requiring or prolonging hospitalization
  - Infection, bleeding, or other expected direct complications of cytopenias due to active underlying leukemia
  - Grade 3 infusion reaction including CRS, if successfully managed clinically and resolves within 7 days without end-organ damage
  - Grade 3 or 4 isolated electrolyte abnormalities that last < 72 hours

- Grade 4 neutropenia or thrombocytopenia lasting  $\geq 42$  days from the start of the cycle in the absence of MDS/AML
- Evidence of drug-induced liver injury based on presence of any of the following abnormalities without an alternate explanation:
  - ALT or AST  $>8x$  ULN
  - ALT or AST  $>5x$  ULN for more than 2 weeks
  - ALT or AST  $>3x$  ULN and (TBL  $>2x$ ULN or INR  $>1.5$ )
  - ALT or AST  $>3x$  ULN with the appearance of fatigue, nausea, vomiting, right upper quadrant pain or tenderness, fever, rash, and/or eosinophilia ( $>5\%$ )

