after every five patients has completed the first cycle of treatment (see tables below). If the accumulated observed data suggests a high chance (i.e., >80% probability) for the “true” toxicity (as defined in Section 11.5) to be >20% for non-GVHD events or 25% for GVHD events, enrollment will be paused and data for assessment of early stopping will be sent to QASMC for review to consider study termination. The following tables show the number of patients with the number of adverse events that would result in a pause of enrollment to assess premature stopping of the trial. The stopping boundaries were obtained using Multc99 version 2.1, a free-download software from M.D. Anderson Cancer Center (<https://trialdesign.org/one-page-shell.html#BTOX>). Specifically, we assume that the parameter  $\theta$  follows a prior distribution of beta (1,1), i.e.,  $\theta$  with mean = 0.5 but with relatively large variability (non-informative prior). Early stopping will be recommended if we observe 2 non-GVHD events out of the first 6 or 2 GVHD events out of first 5 patients, etc. (see Tables below), in patients treated in this trial. A simulation study is also performed to assess the operating characteristics for the above stopping rule (all scenarios are based on 10,000 simulated trials). For non-GVHD events, there will be only 15% chance to stop early if the “true” toxicity rate is 10%. In contrast, we will have 88% chance to stop early (with a median of 10 patients treated) if the “true” toxicity rate on flotetuzumab monotherapy is 30%. For GVHD events, there will be only 21% chance to stop early if the “true” rate is 15% and there will be 86% chance to stop early (with a median of 5 patients treated) if the “true” rate is 35%.

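### The infection/bleeding exception in the non-GVHD stopping rule has no grade limit, so a possibly treatment-related death placed under it is not counted

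*Combined protocol and SAP*

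**What the plan says.** Section 11.5.1 sets the non-GVHD limit with "Excess non-GVHD toxicity will be defined as a combined incidence of > 20% of any of the following". The first item on the list is any event at or above "Grade 3 non-hematologic AE at least possibly attributable to protocol treatment, with the following exceptions". The threshold has no upper end, so Grade 5 is inside it. Five exceptions follow:

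- "Grade 3 fatigue, asthenia, fever, constipation or anorexia" (Grade 3 only, with a condition on anorexia)
- "Grade 3 nausea, vomiting or diarrhea not requiring tube feeding" (Grade 3 only, with further conditions)
- "Infection, bleeding, or other expected direct complications of cytopenias due to active underlying leukemia" (no grade stated)
- "Grade 3 infusion reaction including CRS, if successfully managed clinically and resolves within 7 days without end-organ damage" (Grade 3 only, with limits on time and outcome)
- "Grade 3 or 4 isolated electrolyte abnormalities that last < 72 hours" (Grade 3 or 4, with a time limit)

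The definitions of excess toxicity in Appendix I repeat the same wording. Section 11.6 applies a Bayesian rule to these events. Enrolment pauses for QASMC review when the posterior probability that the toxicity rate exceeds 20% is above 0.80, under a Beta(1,1) prior, with a look after every five patients. The printed boundaries are 2/5, 3/10, 4/15, 5/20 and 6/25. Nothing in Sections 11.5 or 11.6 adds fatal events back once an exception has removed them.

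**The concern.** The exceptions can only act on events already judged at least possibly related to treatment, because unrelated events never enter the count. The infection/bleeding exception therefore removes events with two candidate causes, treatment and leukemic cytopenia. Having no grade limit, it removes them up to and including death. The documents do not say how an event with both causes should be classified.

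Such events are plausible in this population. Isolated extramedullary relapse is excluded (Section 3.2), so every patient has marrow disease at entry. The design response rates of 10% and 30% (Section 11.3) leave 70% to 90% of patients outside CR/CRi at Cycle 1 Day 28. Treatment includes dexamethasone premedication, and tocilizumab and steroids appear in the management of infusion reactions (Tables 1 and 6). The separate criterion for prolonged Grade 4 cytopenia applies only when MDS/AML is absent, so it does not pick up these patients.

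At stake is whether a safety boundary can stay uncrossed, and enrolment continue, while deaths to which treatment may have contributed accumulate outside the count.

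**Working it through.** **1. Reproduce the plan's own figures.** Inputs from Section 11.6 and its table: looks at n = 5, 10, 15, 20, 25 and printed boundaries 2, 3, 4, 5, 6. The method is an exact binomial recursion: carry forward the probability of each event count still below the boundary, add five new patients at each look, and sum the probability of first crossing, including a crossing at 25.

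At a true rate of 30%, the first look gives 1 − 0.7^5 − 5(0.3)(0.7^4) = 1 − 0.168 − 0.360 = 0.472. First-crossing probabilities over the five looks are 0.472, 0.197, 0.106, 0.065 and 0.042, a total of 0.882 (plan: 88%). The cumulative value passes one half at n = 10 (0.472 + 0.197 = 0.669), which matches the stated median of 10. At a true rate of 10% the total is 0.143 (plan: 15%).

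**2. What one death does at the first look.** With x events in n patients the posterior is Beta(1 + x, 1 + n − x). Then Pr(θ > 0.20) = Pr(Bin(n + 1, 0.20) ≤ x).

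- x = 2, n = 5: 0.8^6 + 6(0.2)(0.8^5) + 15(0.2^2)(0.8^4) = 0.262 + 0.393 + 0.246 = 0.901, above 0.80, so enrolment pauses.
- x = 1, n = 5: 0.262 + 0.393 = 0.655, below 0.80, so it does not.

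The decision turns on how one fatal infection is classified, if that patient has no other counted event.

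**3. Effect on the chance of crossing.** The documents give no rate for fatal events under the exception, so this is an assumption shown as a range. Let the true rate of related qualifying toxicity be 30%, and let d percentage points be fatal events under the exception in patients with nothing else counted. The counted rate is then 30% − d.

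| d (assumed) | Counted rate | Chance of crossing |
|---|---|---|
| 0 | 30% | 88.2% |
| 1 | 29% | 86.2% |
| 2 | 28% | 83.9% |
| 3 | 27% | 81.3% |
| 4 | 26% | 78.5% |
| 5 | 25% | 75.4% |

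**4. The price of counting them.** The same recursion at low counted rates gives 14.3% at 10%, 17.6% at 11% and 21.3% at 12%. Each extra point counted adds 3 to 4 points to the chance of a pause.

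The printed boundaries are used throughout because they reproduce the plan's stated probabilities. The printed limits at 15, 20 and 25 have posteriors of 0.798, 0.769 and 0.747, below the 0.80 criterion. That is a separate matter and does not affect step 2.

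**The case against.** The strongest reply is that the exception is limited by cause. Infection and bleeding are named as examples of expected, direct complications of cytopenias, and those cytopenias must come from active leukemia. Untreated median survival after relapse is put at 2 to 4 months (Section 1.1.1), so deaths from disease are to be expected. Keeping them out of a treatment-toxicity rule is a defensible aim.

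This reply defeats three stronger readings that a reader might infer:

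- **Related deaths from infection or hemorrhage are never counted.** The text does not support this. Such a death still counts if it is not a complication of leukemic cytopenia, for example in remission, with treatment-caused cytopenia, or after immunosuppression for CRS or GVHD. Other related Grade 5 non-hematologic events also count.
- **Two possibly related fatal infections in the first five patients give a count of zero.** That holds only if both are also judged direct complications of leukemic cytopenia.
- **A fall from 88% to 75% measures the defect.** It rests on an assumed 5 points for which the documents give no basis.

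Deaths are also visible elsewhere: SAE reports go to the manufacturer within 24 hours (Section 13.3), unexpected fatal suspected reactions go to the FDA within 7 days (Section 13.4), and the DSM tables list vital status and cause of death. None of these is tied to an enrolment pause, however. The QASMC report is semi-annual (Section 12.0). At 15 to 20 patients a year (Section 1.4), six months is 7.5 to 10 patients, against a look every five under the stopping rule.

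What remains is that the causal limit does not settle an event with two causes, and those are the only events the exception can remove.

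**Conclusion.** The point holds in limited form. The infection/bleeding exception alone among the five has no grade limit. A Grade 4 or 5 event placed under it leaves the non-GVHD count even when treatment may have contributed, and nothing in Sections 11.5 or 11.6 restores a death.

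The first-look example needs no assumed event rate, only that the patient who dies has no other counted event. The loss in crossing probability, from 88% to between 86% and 75%, is an illustration. It depends on a true rate of 30% and on 1 to 5 points of it being fatal events under the exception. The documents cannot say where in that range, or outside it, the trial would fall. The case for a change rests on the gap in the definition and the low cost of closing it, not on a demonstrated loss of that size.

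**What to change.** In Section 11.5.1 and in the matching definitions in Appendix I, add one sentence: any Grade 5 event judged at least possibly attributable to protocol treatment is counted, notwithstanding the infection/bleeding exception. Leave the exception in place for non-fatal events. Grade 4 events under it would still be exempt, so the change restores only the fatal share, and expected non-fatal complications of leukemia would not trip the boundary.

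No new data are needed: attribution is already required to apply the definition, and deaths are recorded on the Death Form (Section 9.0). The cost is a higher chance of a pause when disease and treatment both contribute to a death, at the rates given in step 4 of the working. A crossing leads to a pause and QASMC review, not automatic closure.

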### 11.5.2 Excess GVHD toxicity

Excess GVHD toxicity will be defined as a  $> 25\%$  incidence of Grade III-IV acute GVHD or severe chronic GVHD occurring at any time during treatment.

## 11.6 Stopping rules for safety

A Bayesian sequential monitoring rule will be implemented for safety. The stopping rule is defined as  $\Pr(\theta > \theta_T | \text{data}) > 0.8$ , where  $\theta$  denotes the proportion of toxicities (as defined in Section 11.5) and  $\theta_T$  denotes the expected serious toxicity rate for study treatments (set as  $\theta_T = 20\%$  for non-GVHD toxicity and  $25\%$  for GVHD toxicity). Interval analyses will be performed after every five evaluable patients (see 11.8 for patient evaluability). If the accumulated observed data suggests a high chance (i.e.,  $>80\%$  probability) for the “true” toxicity (as defined in Section 11.5) to be  $>20\%$  for non-GVHD events or  $25\%$  for GVHD events, enrollment will be paused and data for assessment of early stopping will be sent to QASMC for review to consider study termination. The following tables show the number of patients with the number of adverse events that would result in a pause of enrollment to assess premature stopping of the trial. The stopping boundaries were obtained using Multic99 version 2.1, a free-download software from M.D. Anderson Cancer Center (<https://trialdesign.org/one-page-shell.html#BTOX>). Specifically, we assume that the parameter  $\theta$  follows a prior distribution of beta (1,1), i.e.,  $\theta$  with mean = 0.5 but with relatively large variability (non-informative prior). Early stopping will be recommended if we observe 2 non-GVHD events out of the first 6 or 2 GVHD events out of first 5 patients, etc. (see Tables below), in patients treated in this trial. A simulation study is also performed to assess the operating characteristics for the above stopping rule (all scenarios are based on 10,000 simulated trials). For non-GVHD events, there will be only 15% chance to stop early if the “true” toxicity rate is 10%. In contrast, we will have 88% chance to stop early (with a median of 10 patients treated) if the “true” toxicity rate on flotetuzumab monotherapy is 30%. For GVHD events, there will be only 21% chance to stop early if the “true” rate is 15% and there will be 86% chance to stop early (with a median of 5 patients treated) if the “true” rate is 35%.

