**Stopping rules for non-GVHD toxicity:**

# Patients treated	5	10	15	20	25
Stop if the # Grade <math>\geq</math> 3 non-hematologic toxicity	2	3	4	5	6

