**12.0 DATA AND SAFETY MONITORING**

In compliance with the Washington University Institutional Data and Safety Monitoring Plan, the Principal Investigator will provide a Data and Safety Monitoring (DSM) report to the Washington University Quality Assurance and Safety Monitoring Committee (QASMC) semi-annually beginning six months after accrual has opened (if at least one patient has been enrolled) or one year after accrual has opened (if no patients have been enrolled at the six-month mark).

The Principal Investigator will review all patient data at least every six months, and provide a semi-annual report to the QASMC. This report will include:

- HRPO protocol number, protocol title, Principal Investigator name, data coordinator name, regulatory coordinator name, and statistician
- Date of initial HRPO approval, date of most recent consent HRPO approval/revision, date of HRPO expiration, date of most recent QA audit, study status, and phase of study
- History of study including summary of substantive amendments; summary of accrual suspensions including start/stop dates and reason; and summary of protocol exceptions, error, or breach of confidentiality including start/stop dates and reason
- Study-wide target accrual and study-wide actual accrual
- Protocol activation date
- Average rate of accrual observed in year 1, year 2, and subsequent years
- Expected accrual end date
- Objectives of protocol with supporting data and list the number of participants who have met each objective
- Measures of efficacy
- Early stopping rules with supporting data and list the number of participants who have met the early stopping rules
- Summary of toxicities
- Abstract submissions/publications
- Summary of any recent literature that may affect the safety or ethics of the study

The study principal investigator and Research Patient Coordinator will monitor for serious toxicities on an ongoing basis. Once the principal investigator or Research Patient Coordinator becomes aware of an adverse event, the AE will be reported to the HRPO and QASMC according to institutional guidelines.

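### The safety rule does not pause enrollment when the event count has already reached the next look's boundary, so up to three more patients per block of five may start treatment

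*Combined protocol and SAP*

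**What the plan says.** Section 11.6 fixes when the safety data are examined: "Interval analyses will be performed after every five evaluable patients (see 11.8 for patient evaluability". Appendix I puts the same looks "after every five patients has completed the first cycle of treatment". The two texts differ on what makes a patient count, but both use steps of five.

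The tables in Section 11.6, repeated in Appendix I, give event counts at 5, 10, 15, 20 and 25 patients. The non-GVHD row reads "non-hematologic toxicity 2 3 4 5 6"; the GVHD row is 2, 4, 5, 6 and 8. Reaching a boundary pauses enrollment and sends the data to QASMC, which considers termination. It is not an automatic stop.

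Other parts of the plan bear on the time between looks:
- Section 9.0 has the Toxicity and Stopping Rules forms submitted continuously.
- Section 12.0 says: "The study principal investigator and Research Patient Coordinator will monitor for serious toxicities on an ongoing basis". It attaches no count to this.
- Section 11.6 and Appendix I also recommend early stopping at 2 non-GVHD events among the first 6 patients. Six is not on the grid, and no boundary in the table corresponds to it.

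**The concern.** The number of patients with a confirmed qualifying event can only rise. If patients 1 and 2 both have one, the boundary of 2 at the first look is already met, whatever happens to patients 3 to 5. Nothing in Section 11.6 or Appendix I holds enrollment at that point.

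Section 11.5 gives limiting risk to patients as the purpose of these analyses. Sections 1.2.1 and 6.4 say the drug has not been evaluated after allo-HCT and that its effect on GVHD there is unknown. In a trial of 25, one to three patients who start after the pause is certain are a real share of the exposure the rule is meant to limit.

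**Working it through.** **Inputs.** Printed boundaries at 5/10/15/20/25: non-GVHD 2/3/4/5/6, GVHD 2/4/5/6/8. True rates used in Section 11.6: 10% and 30% (non-GVHD), 15% and 35% (GVHD). Maximum 25 patients (Section 11.3). Accrual 15–20 per year (Section 1.4).

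**Step 1: reproduce the plan's figures.** Exact binomial recursion, with looks at the five grid points only and a crossing at 25 counted as a stop:

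| Rule, true rate | Stated | Recomputed |
|---|---|---|
| Non-GVHD, 10% | 15% | 14.3% |
| Non-GVHD, 30% | 88%, median 10 | 88%, median 10 |
| GVHD, 15% | 21% | 21.1% |
| GVHD, 35% | 86%, median 5 | 85.7%, median 5 |

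The medians follow from the cumulative crossing probabilities. Non-GVHD at 30%: 0.472 by patient 5 and 0.669 by patient 10. GVHD at 35%: 0.572 by patient 5. Five-patient looks are therefore the design whose properties the plan reports.

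**Step 2: most patients who can start after crossing is certain.** A trial that passes a look has at most (boundary − 1) events. The fewest further events needed is the next boundary minus that number, and the rest of the five patients are avoidable.
- Non-GVHD: two further events are needed in every block, so 5 − 2 = 3.
- GVHD: 3 in the blocks ending at 5, 15 and 20. In the block ending at 10 it is 5 − (4 − 1) = 2, and in the block ending at 25 it is 5 − (8 − 5) = 2.

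**Step 3: expected number.** Suppose r more events are needed in a block. The r-th falls on the block's j-th patient with probability C(j−1, r−1) p^r (1−p)^(j−r), and 5 − j patients are then avoidable. First non-GVHD block at p = 0.30, r = 2:
- j = 2, 3, 4, 5: 0.0900, 0.1260, 0.1323, 0.1235. The sum is 0.4718, which equals the probability of crossing at the first look.
- Avoidable: 3(0.0900) + 2(0.1260) + 1(0.1323) = 0.654.
- Crossing is certain by patient 3 in 0.0900 + 0.1260 = 21.6% of all trials.

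Summed over all five blocks:

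| Rule, true rate | First pause | Saved per trial | Saved per pausing trial | Mean patients at pause |
|---|---|---|---|---|
| Non-GVHD, 10% | 14.3% | 0.15 | 1.06 | 8.87 → 7.81 |
| Non-GVHD, 30% | 88% | 1.17 | 1.33 | 9.38 → 8.06 |
| GVHD, 15% | 21.1% | 0.23 | 1.10 | 7.36 → 6.27 |
| GVHD, 35% | 85.7% | 1.14 | 1.33 | 8.55 → 7.22 |

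At each of the two high rates, 72% of pauses come at least one patient earlier and 43% at least two. Averaged over all trials, patients treated fall from 11.22 to 10.05 (non-GVHD, 30%) and from 10.90 to 9.76 (GVHD, 35%).

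**Step 4: the chance of a first pause.** Curtailment acts only when the next crossing is already certain, so the same trials pause. In 400,000 simulated trials per rate, the two versions paused identical sets.

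**Step 5: reporting delay.** Step 3 assumes each event is known before the next patient starts. Accrual of 15–20 per year is one patient per 365/20 = 18 to 365/15 = 24 days. As a sensitivity check I assumed Poisson accrual at 15 or 20 per year, events spread evenly over the first 14 or 28 days, looks when the last of each five has completed 28 days, and no hold on enrollment meanwhile. The saving at the two high rates is then 1.6 to 2.1 enrollments per trial. The accrual pattern and event timing are assumptions; the documents do not give them.

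**The case against.** **Grouped looks are a legitimate design.** The operating characteristics are disclosed and reproduce. This stands: the plan contains no error here, only a missed refinement.

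**The rule may already act between looks.** One sentence in Section 11.6 ties the pause to the accumulated data without naming a look. With the Beta(1,1) prior, 2 events in 2 patients give Pr(θ > 0.20) = 1 − 0.2³ = 0.992, far above 0.8. The stated figures rule this reading out. Applied after every patient, the formula would already stop at 1 event in 3, where the posterior is 0.8⁴ + 4(0.2)(0.8³) = 0.819, and likewise at 1 in 1 or 1 in 2. At a true rate of 10% that alone would stop 1 − 0.9³ = 27% of trials, against the stated 15%. The 2-of-6 sentence does make the section inconsistent, so a flat claim that the plan acts only at every fifth patient goes too far.

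**A reader might infer that the extra patients yield nothing.** The documents do not support that. Crossing leads to a review, and 2 of 5 and 5 of 5 are different evidence for QASMC. The patients also count toward the 15-patient futility stage in Section 11.4. Only the fact of crossing is settled.

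**A reader might also infer that earlier pausing is free.** The equality in Step 4 covers the first pause only. If QASMC cleared a pause at patient 2 and the scheduled look stayed unchanged, the same two events would meet the boundary again at patient 5. The added wording must deal with this.

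**Events are not always known at once.** Section 11.5.1 excludes a Grade 3 infusion reaction that is managed and resolves within 7 days, and counts Grade 4 cytopenia only from day 42 of the cycle. A provisional event may therefore drop out, so the trigger has to rest on confirmed events.

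**Existing safeguards.** Continuous forms, ongoing monitoring and patient-level holds exist, and nothing obliges the investigator to keep enrolling. None of these is a numeric trigger.

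**Conclusion.** The point holds as a worthwhile, low-cost improvement. As written, up to three patients per block (two in the GVHD blocks ending at 10 and 25) may start treatment after a pause has become certain.

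At the high rates the plan itself considers, the average is about 1.3 per pausing trial, or 1.1 to 1.2 per trial. At the low rates it is 0.15 to 0.23 per trial. The first-pause probability does not change.

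The sizes rest on the printed boundaries, independent patients with a constant event rate, and events confirmed before the next patient starts. They shift with reporting delay, and are less certain for late events such as GVHD.

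**What to change.** Add to Section 11.6 and Appendix I:

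*Enrollment is paused for QASMC review as soon as the number of patients with a confirmed qualifying event (Section 11.5) reaches the boundary for the next scheduled look, without waiting for that look. If QASMC allows enrollment to resume, the same events do not trigger a second pause at that look unless a further qualifying event has occurred.*

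Keep the tables and the scheduled looks. In the same edit, reconcile the sentence on 2 non-GVHD events in the first 6 patients with the table. The new wording does not do this: if the second event falls on patient 6, the next boundary is 3 at patient 10 and no pause follows.

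The cost is two sentences and no new data collection, since the Stopping Rules form is already submitted continuously. The stated stopping probabilities stay valid for the first pause; the quoted medians of patients treated should be recomputed. The downside is that pauses, including false ones, come about one patient earlier and on slightly less data.

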## 1.4 Study Duration and Dates

It is generally expected that ~15-20 patients will be accrued per year. The target accrual for the study is 25 patients. Therefore, it is anticipated that the time from the study opening to completion of accrual will be ~18 months.

Patients will receive the investigational treatment for the first 28 days of the study (Cycle 1). Based on Day 28 response assessment, patients with CR/CRi/PR/SD may continue investigational treatment for another 28 days (Cycle 2); and patients with PD will come off study. All patients will be followed for 2 years after receiving investigational treatment.

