### 5.2.3 Donor Lymphocyte Infusion (DLI)

Patients with available donor cells may receive a donor lymphocyte infusion during Cycle 1 and/or Cycle 2 (if given) at the discretion of the investigator and the treating physician.

- DLI should be administered on or after Day 8 of Cycle 1 and/or Cycle 2

- Cell dose of DLI will vary depending on donor source at the discretion of the treating physician and according to institutional practices:
  - For matched unrelated donors and matched related donors DLI containing a range of  $0.5 \times 10^7$  to  $1.0 \times 10^8$  CD3+ cells/kg will be administered.
  - For haploidentical and mismatched donors DLI containing a range of  $0.5 \times 10^6$  to  $1.0 \times 10^7$  CD3+ cells/kg will be administered.

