### 5.5 Definitions of Evaluability

Endpoint	To be evaluable for this endpoint, a patient must...
Efficacy (CR and CRi, C1D28 assessment)	Have completed all Cycle 1 infusions of flotetuzumab (or discontinued treatment due to drug toxicity or disease progression). Patients who are not evaluable for the primary objective will be replaced.
Efficacy (CR and CRi, C2D28 assessment)	Have completed all Cycle 1 and 2 infusions of flotetuzumab (or discontinued treatment due to drug toxicity or disease progression) and undergone C2D28 disease assessment
Efficacy (ORR defined as PR or greater)	Have completed all Cycle 1 infusions of flotetuzumab (or discontinued treatment due to

Efficacy (MLFS rate)	drug toxicity or progression) and undergone C2D28 disease assessment (or C1D28 assessment for patients who only received Cycle 1 treatment).
Efficacy (PR rate)	
Efficacy (SD rate)	
Efficacy (PFS)	
Efficacy (OS)	Have undergone any period of infusion of flotetuzumab
Safety and tolerability (AEs by CTCAE)	
Safety and tolerability (CRS and neurotoxicity by ASTCT)	
Safety and tolerability (acute GVHD by MAGIC criteria)	
Safety and tolerability (chronic GVHD by NIH severity score)	

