**11.8 Analysis Populations**

Safety analysis will include all patients who receive at least one dose of treatment drug.

Efficacy analysis will include patients who complete at least 1 cycle of treatment or patients who withdraw before completing Cycle 1 for a reason at least possibly related to drug toxicity.

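### Section 11.6 with 11.8 sets no observation time before a patient counts at a safety look, Appendix I does, and the stated 88% and 86% chances of stopping hold only with full observation

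*Combined protocol and SAP*

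**What the plan says.** Section 11.6 sets a Bayesian rule with a Beta(1,1) prior: enrolment is paused for QASMC review when the posterior probability that toxicity exceeds 20% (non-GVHD) or 25% (GVHD) is above 0.8. On timing it says "Interval analyses will be performed after every five evaluable patients (see 11.8 for patient evaluability").

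Section 11.8 does not define the word evaluable. Its safety sentence reads "Safety analysis will include all patients who receive at least one dose of treatment drug"; its efficacy sentence begins "Efficacy analysis will include patients who complete at least 1 cycle of treatment". The safety rows of Section 5.5 agree with the first of these: "Have undergone any period of infusion of flotetuzumab". Both boundary tables are indexed by the number of patients treated.

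Appendix I repeats the rule, boundaries and stopping chances, but times the looks "after every five patients has completed the first cycle of treatment (see tables below").

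The stated performance is an 88% chance of stopping for non-GVHD toxicity at a true rate of 30% and, for GVHD at a true rate of 35%, "86% chance to stop early (with a median of 5 patients treated"). Section 11.5.2 counts GVHD at any time during treatment. Section 11.5.1 includes a cytopenia event that needs at least 42 days from the start of the cycle.

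**The concern.** The main text and the appendix give different dates for the same look. Under 11.6 read with 11.8 and 5.5, a patient can enter the denominator on the day of the first dose. Treatment lasts 28 days, or 56 with Cycle 2, and several qualifying events come late. On donor lymphocytes, Section 5.2.3 says "DLI should be administered on or after Day 8 of Cycle 1 and/or Cycle 2", so GVHD caused by such an infusion cannot appear in the first week.

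A patient who is counted but hardly observed adds to the denominator and almost nothing to the numerator. If looks were run that way, an excessive toxicity rate would be found later and less often than the protocol tells its monitoring committee. The effect is greatest at the first look. It also matters because Sections 1.2.1 and 6.4 describe the GVHD risk of flotetuzumab after transplant as unknown.

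**Working it through.** **Inputs.** Printed boundaries for looks at 5, 10, 15, 20 and 25 patients: 2, 3, 4, 5, 6 events (non-GVHD) and 2, 4, 5, 6, 8 (GVHD), from 11.6. Accrual from Section 1.4: "15-20 patients will be accrued per year". Onset timing is not in the documents, so uniform windows are assumed.

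**Step 1: reproduce the stated figures.** With every outcome known at each look, add five Binomial(5, p) outcomes per stage and remove the paths that cross. The cumulative chances of crossing are:

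| Look | Non-GVHD, p = 0.30 | GVHD, p = 0.35 |
|---|---|---|
| 5 | 47.2% | 57.2% |
| 10 | 66.9% | 65.1% |
| 15 | 77.5% | 76.0% |
| 20 | 84.0% | 83.8% |
| 25 | 88.2% | 85.7% |

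The plan states 88% and 86%. At the acceptable rates of 10% and 15% the same recursion gives 14.3% and 21.1%, against the stated 15% and 21%. The plan's figures therefore assume complete observation.

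**Step 2: how many patients are immature.** At 15-20 per year, the expected number of earlier patients who started in the last 28 days is 15 × 28/365 = 1.2 to 20 × 28/365 = 1.5, plus the newest patient. For a 56-day window these figures double to 2.3-3.1.

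**Step 3: first look by hand.** The boundary is 2 events. If m of the five patients are effectively observed, the chance of crossing is 1 − (1−p)^m − m·p·(1−p)^(m−1).

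- Non-GVHD, p = 0.30: m = 5 gives 1 − 0.168 − 0.360 = 47%; m = 4 gives 1 − 0.240 − 0.412 = 35%; m = 3 gives 1 − 0.343 − 0.441 = 22%.
- GVHD, p = 0.35: m = 5 gives 1 − 0.116 − 0.312 = 57%; m = 4 gives 1 − 0.179 − 0.384 = 44%; m = 3 gives 1 − 0.275 − 0.444 = 28%.

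**Step 4: whole trial by simulation.** Random arrivals at 15 or 20 per year, look on the day of the nth first dose, printed boundaries, and events counted only if onset precedes the look. Events missed at one look count at later ones.

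| Assumed onset | First look | All five looks | Look at 25 allowed to mature |
|---|---|---|---|
| Non-GVHD, Day 1-7 | 32-33% | about 84% | about 86% |
| Non-GVHD, Day 1-28 | 25-27% | 82-83% | about 86% |
| GVHD, Day 8-28 | 29-33% | 75-77% | about 80% |
| GVHD, Day 8-56 | 20-25% | 71-74% | about 78% |

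For GVHD with onset Day 8-28, cumulative crossing is 42-45% by patient 10 and 59-61% by patient 15. On this reading the median is therefore the look at 15, not the stated 5.

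**Step 5: Appendix I timing.** With each look 28 days after the nth first dose, the chances return to 88% and 86% for events within Cycle 1. For GVHD they are about 79-82% if onset runs to Day 56-70.

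**The case against.** A reader might infer that 11.6 scores unobserved patients as event-free, so that 88% and 86% are simply not delivered. The documents do not go that far. No passage gives a scoring rule for a patient still under observation, and none fixes the look on the day of the nth first dose. The 11.8 safety sentence defines an analysis set, not a date. Section 11.7 ties evaluability for the primary objective to Cycle 1, and Appendix I requires Cycle 1 completion outright. On that reading the stated figures hold for Cycle 1 events. Section 11.6 also speaks of events among the first five patients, which can be read as a count on a fixed group whenever its events appear. Section 9 collects the stopping-rules form continuously.

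The size is open to challenge too. Accrual is complete at patient 25, so nothing prevents that look from maturing. Infusion reactions typically came within 48 hours (Section 1.2.1), which favours the early-onset row. Donor lymphocytes are optional, and patients with progressive disease leave after Cycle 1, so not everyone is at risk to Day 56. Crossing a boundary pauses enrolment for review; it does not close the trial.

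All of this stands and limits the claim. It does not remove the gap: 11.6 points to a section whose only safety criterion is one dose, 5.5 agrees, the tables count patients treated, and the one text that sets a window is a reporting appendix that differs from the section it restates.

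**Conclusion.** The concern holds as an unresolved conflict with a measurable consequence. The protocol gives two triggers for one rule, and only the Appendix I trigger supports 88% and 86%, and then only for events within Cycle 1. Under the trigger that 11.6 and 11.8 permit, the loss by the end of the trial, with the look at 25 mature, is about 2 points for non-GVHD and 6 for GVHD (8 if onset runs to Day 56). With that look immature as well, it is 4-6 points and 9-11 points (12-15 to Day 56). Much of the effect is later detection: at the first look the chance of a pause falls by roughly a third to a half.

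These sizes rest on accrual of 15-20 per year, uniform onset, looks at first dose, and no event credited to patients still under observation. The last two are inferences from silence in the text.

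**What to change.** Reconcile 11.6 and 11.8 with Appendix I in a few sentences, used word for word in both places:

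- Define each look on the first 5, 10, 15, 20 and 25 treated patients in order of entry.
- Trigger the planned enrolment pause and QASMC review as soon as the boundary count in that group is reached.
- Declare a look passed only when every patient in the group has had an event or been observed to the end of Cycle 1. State how a patient who dies or is lost before then is scored.
- Carry later events (Cycle 2 GVHD, cytopenia of at least 42 days) to the next look.
- State that 88% and 86% apply to events within Cycle 1, with about 79-82% for GVHD if onset runs to Day 56-70. Otherwise, recompute the chances for whichever rule is kept.
- Restate the median number treated. Enrolment continues during observation, so the GVHD median becomes about 6 rather than 5 for onset Day 8-28.

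Cost: a look without a crossing closes up to 28 days later. The chance of a false pause is the stated 15% and 21%, rather than about 9-11% (non-GVHD) and 11-12% (GVHD, onset Day 8-28) under the immature count. No extra patients or assessments are needed.
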